 6. Good general and oral health

- Exclusion Criteria:** for the involved subjects included:
 1. Patients suffering from any systemic diseases interfering with tooth movement.
 2. Patients with extracted or missing permanent teeth. (except for third molars).
 3. Patients with badly decayed teeth.
 4. Patients with any parafunctional habits (i.e. Bruxism, tongue thrusting, mouth breathing, etc...).
 5. Patients with previous orthodontic treatment

C] Interventions:

➤ **Medical History Questionnaire:**

For every patient, to exclude the presence of any systemic condition interfering with orthodontic treatment.

➤ **Clinical Examination:**

Oral structures will be examined to identify caries, fracture or missing teeth. Gingival tissues will be carefully examined for any gingivitis, periodontitis, recession, or lesions.

➤ **Diagnosis**

Check the potential patient to fulfill the previously mentioned inclusion criteria. Every participant will be asked to sign an informed consent about the study. Full set of records (study models, panorama radiograph and lateral cephalometric radiographs, photos) will be taken for every patient as part of the routine procedure for treatment of patients in the clinic of the Orthodontic Department, Future University.

➤ **Clinical Procedure:**

After taking pre-treatment records, every patient will receive:

- Bonding of all teeth except for first premolars and banding/bonding the first and second molars will be done using Roth prescription brackets (0.022 x 0.028 slot)*.
- Miniscrews** will then be placed in the upper arch between the second premolar and first molar.

*American Orthodontics

** Jeil Miniscrews

- The patient will be referred for extraction of first premolars.
- Anchorage will be secured, followed by Leveling and alignment for the bonded and banded teeth through following the wire sequence: 0.014 NiTi, 0.016×0.022 NiTi and 0.017×0.025 StSt.
- After levelling and aligning is completed (right before retraction), the patient will be referred for the uptake of pre-intervention records.

➤ **Acquisition of pre-intervention records:**

- The patient will be referred for the uptake of a Lateral Cephalometric radiograph, which will be considered the T0 record.
- Impressions will be taken before retraction (without the archwire in place) followed by digital scanning of produced models.

➤ **Begin of Retraction:**

Frictionless group:

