- A ligature wire extended between the second premolars and miniscrews will be used for proper anchorage control.
- Closing retraction T-loops will be fabricated using 0.017 x 0.025 TMA wire. The loop will be positioned halfway the extraction space and the canine.^{35,36}.
- A gable angle of 45° will be added.
- Distal activation of 4 mm will be done with cinch back the wire distal to 2nd molars bilaterally.³⁷

Friction group:

- Crimpable hooks added to the arch wire (0.017"x0.025" Stainless steel) distal to the lateral incisor passing near the center of resistance of the anterior segment.
- Retraction will start on a 0.017"x0.025" Stainless steel wire using elastomeric chain (force applied will be 212 g per side)³⁸ extending between the crimpable hooks and the miniscrew.
- The force will be measured by a force gauge and reactivated every 4 weeks maintaining constant force of retraction all over the retraction phase.

➤ **Follow up visits**

Patients will be asked to attend for follow up sessions every 4 weeks for:

- Evaluation miniscrews stability.
- Replacement of the power chain to maintain a force of 212 gm per side.
- Reactivation of the T-loop by further distal activation and cinch back.
- Impression taking to determine the overall rate of retraction.

➤ **Criteria for discontinuing or modifying the allocated intervention:**

In cases of prolonged swelling or pain related to the miniscrew, the patient will be given strict oral hygiene measures and may wait for three weeks before the beginning of retraction.

In cases of loose or broken miniscrews, the screw will be removed and replace the miniscrew after complete resolution of the inflammation.

□ **Post-retraction Questionnaire:**

The patients of both groups will be asked to fill in questionnaires regarding their experience with their allocated technique

□ **Retraction records**

Following en-masse, patients will be referred to the same radiology center to acquire the final lateral cephalometric x-ray to assess the movement and inclination of anterior teeth.

The final dental model will assess the rate of retraction, molar rotation, and molar anchorage loss achieved throughout the study.

□ **Material Used**

- American Orthodontics Brackets, Roth prescription, 22 slot size.
- American Orthodontics Elastomeric power chains
- American Orthodontics Elastomeric O-ties
- American Orthodontics Ligature wire.

- Jiel Miniscrew, 8 mm TAD
- American Orthodontics Arch wires.

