Blinding of the operators: Blinding will not be possible for the operators during the application interventions and during the follow up visits. The principal operator is responsible for assigning subjects to interventions according to the concealed allocation, appliance activation at follow up visits, dental impressions and acquisition of dental casts.

Blinding of the outcome assessors: It is a single blinded study, therefore, only the outcome assessors will be blind. The patients name will be sealed from pre and post radiographs and study models. Then two assessors will carry out, blindly and independently, the measurements and analysis of the study.

III) Data collection, management and analysis:

A] Data collection methods:

Primary outcome:

1. Retraction rate: to assess the antero-posterior movement of anterior teeth and first molars, the principle investigator will take study models for every participant monthly during the follow up visits. Then, The models will be digitalized and the landmarks, reference lines and planes will be identified on the pre, interim and post-retraction digital dental models for measurements reading.

Secondary outcomes

1. Anchorage loss: will be accessed by the principal investigator via digitalized dental models taken before and after the completion of retraction by identifying the landmarks, reference lines and planes, then will interpret the measurements in millimeters.

2. Molar Rotation: will be accessed by the principal investigator via digitalized dental models. These records will be taken before and after the completion of retraction by identifying the landmarks, reference lines and planes, then will interpret the measurements of the angles in degrees.

3. Pain: Each patient will fill a questionnaire regarding his treatment experience in a VAS scoring from 1-10. The questionnaire will include several questions related to oral hygiene, pain and discomfort experienced throughout the trial.

4. Anterior teeth torque, extrusion/intrusion: will be accessed by the principle investigator via lateral cephalometric radiographs taken before and after the completion of retraction. The principal investigator will identify the landmarks, reference lines and planes, then will interpret the measurements in degrees and millimeters.

B] Data management:

A colleague outside the research team will enter the data and organize it in excel sheets in the computer of the orthodontic department.

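### Sealing the patient's name does not hide the arm: the plan leaves open whether arm-specific hardware shows on the T1 cephalogram and later models, and it conflicts on who measures

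*Combined protocol and SAP*

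**What the plan says.** **Blinding.** Section II) D] states: "It is a single blinded study, therefore, only the outcome assessors will be blind". It rules out blinding of the operators. Masking of the records is described in one sentence, "The patients name will be sealed from pre and post radiographs and study models", followed by "Then two assessors will carry out, blindly and independently, the measurements and analysis of the study". Section V) D] (Confidentiality) adds that data and forms carry a coded ID.

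**Hardware** (Begin of Retraction). For the frictionless arm: "Closing retraction T-loops will be fabricated using 0.017 x 0.025 TMA wire" and "A ligature wire extended between the second premolars and miniscrews will be used for proper anchorage control". The friction arm has hooks crimped to a stainless steel wire, with elastomeric chain running to the miniscrew.

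**Records.**
- T0 models (Acquisition of pre-intervention records): "Impressions will be taken before retraction (without the archwire in place".
- Interim models (Follow up visits, every 4 weeks): "Impression taking to determine the overall rate of retraction", with no word on the wire.
- T1 cephalogram (Retraction records): "patients will be referred to the same radiology center to acquire the final lateral cephalometric x-ray", with no word on the wire.
- T1 model (Retraction records): used for rate, molar rotation and anchorage loss, with no word on the wire.

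**Who measures.** Section III) A] (Data collection methods) names the principal investigator as the reader for anchorage loss, molar rotation and the cephalometric outcomes. Section III) C] (Statistical Analysis) has the same role extract the data from the images and from the models of every visit. Step 5 of the Participant timeline has this role allocate patients to the groups.

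**The concern.** The name is not what identifies the arm. A loop, or a hook, visible on a film or scanned model identifies it whatever label is covered. The outcomes rest on landmarks and reference lines that a person identifies, and the introduction states an expectation in one direction, namely that loops should retract faster. A reader who can see the arm may shift landmarks in that direction without intending to.

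The planned reliability checks would not reveal this. The ICC, the kappa and the one-millimetre disagreement rule (Assessors Reliability) measure agreement between and within examiners. If both examiners see the hardware and lean the same way, agreement stays high.

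At stake is the trial's only blinding: for torque and vertical position through the T1 cephalogram, and possibly for space closure, anchorage loss and molar rotation through the models.

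**Working it through.** **Step 1. Set each record against what the plan says about the appliance.**

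| Record | Outcomes it serves | Condition stated | Can it show the arm? |
|---|---|---|---|
| T0 models | All model outcomes (baseline) | Archwire out | No |
| T0 cephalogram | Torque, vertical position (baseline) | Taken just before retraction, after a levelling wire sequence common to both arms | No arm-specific hardware described by then |
| Interim models | Rate of space closure | None | Yes, if the T0 condition is not repeated |
| T1 models | Rate, anchorage loss, rotation | None | Yes, if the T0 condition is not repeated |
| T1 cephalogram | Torque, vertical position | None | Yes, if taken with the appliance in place |

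The interim models matter because section III) A] places landmarks on the pre, interim and post-retraction models for the primary outcome.

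**Step 2. List the masking steps.** There are two: the sealed name and the coded ID. Both remove identity and neither removes the hardware. No section describes a standard appliance condition after T0, a random reading order or a check of blinding.

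**Step 3. Compare the sections on who measures.** The Blinding section gives the measurements to two blinded, independent assessors. Data collection methods gives anchorage loss, rotation, torque and vertical position to the principal investigator, and Statistical Analysis gives this role the data extraction. The Participant timeline has the same role allocate patients. These statements cannot all hold. For the primary outcome, Data collection methods names no landmark reader, so the conflict reaches it only through the extraction step.

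**Step 4. Size.** The documents give no figure for reader bias, so its size cannot be estimated. The calculation below shows only how sensitive a trial of this size would be to an assumed bias.

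Inputs from the Sample size calculation: SD 0.76, difference 1.0 (unit not stated), power 0.8, alpha 0.05 (two-sided assumed), two independent groups.

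The plan's own figure first: n per group = 2(z₀.₉₇₅ + z₀.₈₀)² × SD² / difference² = 2 × (1.960 + 0.842)² × 0.76² / 1.0² = 9.07, rounded up to 10. The exact noncentral t calculation gives 10.12, with power 0.795 at 10 per group. The stated 10 per group is reproduced.

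Now suppose no true difference and a systematic between-arm reading shift b, in the same unit as the SD. The noncentrality is b / (0.76 × √(2/n)). The denominator is 0.76 × √(2/10) = 0.340 with 10 per group and 0.76 × √(2/15) = 0.278 with 15. The chance of a false-positive result at a nominal two-sided 5% is then:

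| Assumed shift b | 10 per group | 15 per group |
|---|---|---|
| 0.1 | 5.9% | 6.4% |
| 0.2 | 8.6% | 10.7% |
| 0.3 | 13.3% | 18.1% |
| 0.5 | 28.6% | 41.3% |

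Every b is an assumption. The table applies only to an outcome with the planning SD, so not to torque, which is in degrees.

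**The case against.** The strongest reply is that no section says the arm-specific wire is in place on any record after T0. The investigators show that they take outcome impressions with the archwire out, and the plan treats the pre, interim and post models as one series read with common landmarks. A fair reader may conclude that the method was stated once and not repeated. This stands as a limit: for the models, the gap may be one of wording. It does not cover the cephalogram, because the archwire-out instruction concerns impressions only.

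A second reply is that section D] Outcomes defines every outcome as a T0-to-T1 difference, so interim models need not drive the primary comparison. This also stands in part. The outcome table and Data collection methods do bring in the monthly models, and the T1 model carries the same gap, but the exposure is clearest for the cephalometric secondary outcomes.

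A reader might go further and infer that the patient travels to an outside radiology centre with the appliance in place, so that unblinding is certain. The text says only that patients are referred to the same centre; it gives neither its location nor the state of the appliance.

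Finally, the hardware could be cropped from the images. That would be a poor remedy. The loops sit around the extraction space and canine and the hooks distal to the lateral incisor, the region that the space-closure and anterior-tooth measurements need.

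**Conclusion.** The stated masking does not secure the stated blinding. The T1 cephalogram can reveal the arm, and so can the interim and T1 models if the T0 condition is not carried forward. The T0 records are not affected. This is a gap in the plan and not a documented unblinding.

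A reader might infer that the primary result will be biased, or by how much. The documents do not support either: they give no measure of reader bias, and the shifts tabulated above are assumptions.

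The conflict over who measures is documented in the text and must be settled in the same edit. If the principal investigator, who allocates patients, does the measuring, concealing the hardware restores no blinding. It would go too far to conclude that no blinded reading is planned, since the Blinding section provides for two assessors; the sections contradict one another.

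The point should be corrected before outcome records are read, and preferably before post-T0 records are taken.

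**What to change.** 1. In Follow up visits, Retraction records and Data collection methods, state that interim models, T1 models and the T1 cephalogram are recorded in the same arm-neutral condition as the T0 impressions, with arm-specific wire and attachments not visible. How the appliance is handled to achieve this is for the investigators.
2. Where this is not feasible for a record, report the outcome as not assessor-blinded. Do not crop the region that holds the landmarks.
3. Have someone not involved in measurement prepare coded files and present them in random order. Section V) F] limits data access to the supervisors and the principal investigator, so name this person and the assessors there.
4. Ask each assessor to record a guess of the arm, and report the result by arm.
5. Reconcile the Participant timeline, Blinding, Data collection methods and Statistical Analysis sections on who measures. The two assessors already planned, with no part in allocation or treatment, should make all the measurements.

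The cost is some chair time at record visits and minor file handling. No extra imaging, patients or change of design is needed.

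### The plan promises two blinded assessors, yet its data-collection text has the principal investigator read four of the five secondary outcomes, and it names no reader for the primary outcome

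*Combined protocol and SAP*

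**What the plan says.** Section II) D] Blinding calls the trial single-blind. Operators cannot be masked: "Blinding will not be possible for the operators during the application interventions and during the follow up visits". The protection lies with the readers: "only the outcome assessors will be blind. The patients name will be sealed from pre and post radiographs and study models". It continues: "Then two assessors will carry out, blindly and independently, the measurements and analysis of the study".

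Section III) A] Data collection methods names a different reader for the secondary outcomes. Anchorage loss "will be accessed by the principal investigator via digitalized dental models taken before and after the completion of retraction". For the second outcome: "Molar Rotation: will be accessed by the principal investigator via digitalized dental models". For anterior torque and extrusion/intrusion, read from cephalograms: "The principal investigator will identify the landmarks, reference lines and planes, then will interpret the measurements in degrees and millimeters".

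For the primary outcome, the same section says that "the principle investigator will take study models for every participant monthly during the follow up visits". It then describes landmark placement on the initial, interim and final models in the passive voice, without saying who does it. Section III) C] Statistical Analysis makes the principal investigator responsible for extracting data from the models of every visit.

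**The concern.** Placing landmarks on a digital model or a cephalogram involves judgement, so it matters whether the reader knows the arm. Treatment is open to the operators, and assessor blinding is the only safeguard of this kind that the plan claims. If staff follow the outcome-by-outcome instructions, the reader of most secondary outcomes is a role that the plan also involves in allocation and in the monthly visits. The report could then describe as blinded a set of readings for which blinding was never secured.

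The reliability plan (training, repeat readings, intra-class correlation) does not settle this. It measures how well readings agree, and a reader can be consistent and still lean by arm.

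**Working it through.** No figure in the plan is in dispute, so the check sets the sections side by side and then counts the records affected.

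**1. Who reads each outcome** (outcome table under Aim of the study, against sections II) D] and III) A])

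| Outcome | Record | Reader under Blinding | Reader under Data collection |
|---|---|---|---|
| Rate of space closure (primary) | models | two blinded assessors | not named |
| Anchorage loss | models | two blinded assessors | principal investigator |
| Molar rotation | models | two blinded assessors | principal investigator |
| Vertical position | cephalogram | two blinded assessors | principal investigator |
| Anterior torque | cephalogram | two blinded assessors | principal investigator |
| Pain | patient questionnaire | not applicable | patient |

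Torque and vertical position share one numbered item in section III) A], so three items cover four outcomes: 4 of the 5 secondary outcomes, and every one read from a model or cephalogram. No section says which text prevails, or that the principal investigator is one of the two assessors.

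**2. Would that role know patients' arms?**

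- Participant timeline, item 5, has the principal investigator allocate patients. Section II) C] Implementation gives assignment to the main operator, and section II) D] to the principal operator.
- Section III) A] has the principal investigator take the monthly models at follow-up. Section II) D] gives impressions and casts to the principal operator.
- Under Follow up visits, those visits include replacing the power chain in one arm and, in the other, "Reactivation of the T-loop by further distal activation and cinch back". The arm is therefore evident to whoever takes the impression.

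On the text as written, either task tells the principal investigator patients' arms. Both tasks are also given to the operator, and the documents never equate the two roles.

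**3. Would the records themselves be masked?**

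- Names are sealed on the pre and post records. Interim models are not clearly included.
- Under Acquisition of pre-intervention records, the T0 impression is made with the archwire out and before the arm-specific appliance is placed. T0 models therefore do not show the arm.
- Nothing states that the principal investigator reads only sealed or coded records. Section V) D] Confidentiality provides a coded ID, but ties it to confidentiality and not to reading.

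**4. Primary outcome.** The general promise of two blinded assessors applies. Against it stand an unnamed reader in section III) A] and the extraction duty in section III) C], which could mean measuring or only collating. Both readings are open.

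**5. Records with conflicting readers.** Inputs: 15 per group (Sample size calculation), two groups, two time points (T0 and T1), two record types (model and cephalogram).

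- At 15 per group: 15 × 2 × 2 × 2 = 120 records, of which 60 are T0 and 60 are T1.
- At 10 per group, the number before the dropout allowance: 10 × 2 × 2 × 2 = 80.
- The number of interim models cannot be derived, because the plan does not fix how many visits space closure takes.

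**The case against.** The best defence is that knowing a patient's arm is not the same as knowing the arm of a sealed record. Names are sealed on exactly the T0 and T1 records behind these four outcomes, and the plan does not rule out that the principal investigator is one of the two assessors and reads them sealed. Half of the 120 records (60) are T0 records that predate the arm-specific appliance. The final cephalograms come from a radiology center, so being responsible for T1 records need not mean making them in person. The two tasks that reveal the arm are each assigned elsewhere to the operator.

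Much of this stands. Sealing may mask the reader in part, and the T0 records are weak ground for concern. It cannot be said that the principal investigator would recognise any given record. The role overlap is also a fault of its own that needs reconciling, since it leaves unclear who must not read.

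What does not stand is that the general blinding statement disposes of the matter. The data-collection text is the specific instruction, it covers landmark placement and interpretation and not mere supervision, and no sentence ties that reader to sealed or coded records. Sealing a name does not remove what the reader already knows about the patients.

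**Conclusion.** The contradiction over who reads is real for four secondary outcomes: anchorage loss, molar rotation, anterior torque and vertical position. Followed as written, the single-blind claim is not assured for them. The conclusion assumes that the data-collection text is followed literally and that at least one of the two arm-revealing tasks stays with the principal investigator.

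A reader might infer more than the documents support:

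- **That these outcomes will be read unblinded and are biased.** The documents show that masking is not secured, not that it fails. They give no size or direction for any bias.
- **That the primary outcome is read unblinded.** It is not shown to be. Its reader is unnamed and the extraction wording is ambiguous, so the request there is for clarification.
- **That the principal investigator is the treating operator.** The documents do not say so, and the point does not need it.

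This should be fixed, but it is not a fatal flaw. It touches secondary outcomes and the wording for the primary one, and it leaves the sample size unchanged.

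**What to change.** - **Section III) A], secondary outcomes 1, 2 and 4:** name the two already planned blinded assessors as the readers. Name them also as readers of the T0, interim and T1 models for the retraction rate.
- **Section II) D]:** state that the assessors have no part in allocation, treatment or record-taking, and extend sealing to interim models. Use the existing coded ID, applied before reading by someone outside treatment, for example the outside colleague already planned for data entry.
- **Section III) C]:** reword the extraction duty so that the principal investigator only collates and forwards the assessors' readings.
- **Participant timeline item 5, section II) C], section II) D] and section III) A]:** reconcile who assigns patients and who takes impressions.
- **Fallback:** if the principal investigator must remain a reader of an outcome, have that role read only coded, shuffled records and report the limitation, or drop the blinded-assessment claim for that outcome.

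The cost is wording edits plus coding of about 120 T0 and T1 records at 15 per group, and the interim models. If the principal investigator was meant to be one of the two assessors, someone else must take that reading role unless the fallback is used. Masking may remain incomplete where an appliance is visible on a record, and the report should say so.
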